Study Title: Single Breath Hold MRI

NCT02434471

IRB Review Date: 04/16/2015

1) Protocol Title: Single Breath Hold Abdominal MRI

Short Title: Single BH Abdominal MRI

2) Purpose of the Study: To develop a single breath hold abdominal MRI protocol, and compare the image quality of respiratory triggered 3D T₁-weighted images against conventional breath hold images.

3) Background and Significance: T₁-weighted imaging is a mainstay of abdominal MRI, providing information about both intrinsic tissue properties and lesional vascular properties (when an intravenous contrast agent is administered).

However, T₁-weighted imaging is highly motion-sensitive and typically performed in a breath hold. Particularly in ill patients, such as inpatients and those presenting to the Emergency Department, breath holding capacity may be diminished, and high-quality T₁-weighted imaging may be difficult to obtain. Many motion compensation methods have been developed, including respiratory triggered and radial imaging. However, these methods are, in general, too time-consuming for routine use in dynamic liver MRI, which requires the acquisition of arterial, portal venous, and equilibrium phase images in relatively rapid succession.

Recently, high temporal acceleration factors for T₁-weighted imaging have been combined with respiratory triggering in order to produce respiratory triggered sequences that are more suitable for dynamic imaging; these are based on combining conventional respiratory triggering with optimized versions of the conventional LAVA (Liver Acquisition with Volume Acquisition) pulse sequence. Such a sequence is rapid enough for portal venous and equilibrium phase imaging during free breathing, though not necessarily for arterial phase imaging. This sequence could allow for an optimized liver MRI protocol that could be performed with only one breath hold in the arterial phase, and no additional breath holds, in contrast to the typical examination which typically requires four or more breath holds.

The purpose of this study is to evaluate a single breath hold abdominal MRI protocol, to and compare the image quality of respiratory triggered 3D T₁-weighted images against conventional breath hold images.

4) Design and Procedures: This will be a prospective study with written informed consent obtained. Patients presenting to DUHS for clinical abdominal MRI at the Duke Medical Pavilion (inpatients and emergency department patients) as part of their routine care will be included. In addition to their typical contrast-enhanced abdominal MRI protocol, we will acquire three extra image sets:

- 1) Respiratory-triggered T₁w DISCO LAVA precontrast
- 2) Respiratory-triggered T₁w DISCO LAVA in the portal venous phase

3) Respiratory-triggered T_1 w DISCO LAVA in the equilibrium phase

The only modification to the patients' clinical scan protocol will be to add these three image sets. This is expected to add about 5 minutes to their scan time, and will not significantly affect clinical workflow/throughput. All patients presenting for imaging on the appropriate MRI scanner while a CRC is available to obtain written informed consent, who are able to give consent, will be offered the opportunity to participate in this study. The clinical image data which are routinely sent to PACS will be deidentified and exported for offline analysis, and raw data may be collected in some cases for reprocessing.

Only subjects presenting for clinical MRI will be included. Up to 100 subjects will be included. On data collection, an investigator will assign a serial code number and document pertinent demographic information such as patient age and gender. The code number assigned will not be derived from any personal identifier for the subject. The investigator will also access Maestro records to confirm the indication for the examination and to obtain laboratory values near the time of the examination. The imaging examinations and clinical information will have all patient identifiers removed, including the name, medical record number, and date of birth.

Subsequently, the individual MRI examinations and clinical information will be labeled with a unique assigned code number. After all relevant information is recorded and the exams/reports coded, the investigator will destroy the key linking any subject's personal history information to the assigned code numbers.

Rationale for prospective design: This project would not be possible to perform in a retrospective setting, because clinical rationale for performing the additional T_1 -weighted acquisitions above is lacking.

5) Selection of Subjects: The study population will include up to 100 consecutive subjects undergoing abdominal MRI, age 18 years and older. All subjects regardless of gender or race who had the appropriate imaging will be included. Information will be obtained from electronic records and PACS.

6) Subject Recruitment and Compensation: There will be no financial compensation to subjects as part of this study. Subject recruitment will consist of discussion of the study with potential subjects by the clinical research coordinator or other study team members just prior to the beginning of the examination. The study will be briefly discussed prior to the examination, and if the patient indicates their interest in participating, there will be a more thorough discussion of the study, and a consent form will be provided to the potential subject. Subjects will be provided adequate time to review the consent form and decide whether to participate in the study. If a patient does not wish to participate, they will have their MRI examination per clinical routine.

7) Consent Process: Informed written consent will be obtained from the subjects by the study staff at the time of examination. It will be made clear that if the subject does not wish to

participate in the study, the typical MRI of the liver which had been previously ordered will be performed with no change in care as a result of nonparticipation.

8) Subject Capacity to Give Legally Effective Consent: Only subjects with the capacity to provide written, informed consent, as determined by the study staff.

9) Study Interventions: No interventions will be performed as part of this study.

10) Risk/Benefit Assessment: The only risk of performing this study is the loss of confidentiality in the use of patient data. This is minimized by immediate de-identification of all patient and image data using linking data and destruction of the linking data as soon as possible in the data collection process. The remaining data will only be retained in a password-protected folder on a research shared drive supported by DHTS. The benefits of performing this study include improving our understanding of liver nodule characteristics.

Please note that the pulse sequences used in this study (standard LAVA and respiratory-triggered DISCO LAVA) are FDA/510k cleared and are to be used within the FDA-cleared parameters. Thus, we believe that no IDE or IDE exemption is needed.

11) Costs to the Subject: There will be no costs to any subjects.

12) Data Analysis and Statistical Considerations: Up to 100 subjects will be included in the study population.

Two investigators will independently evaluate MRI examinations. They will assign motion scores and other measures of image quality between respiratory triggered and corresponding breath hold acquisitions. Comparisons between motion scores as well as other image quality scores will be made using the Wilcoxon rank sum test. Inter-reader agreement will be assessed using the Interclass Correlation Coefficient.

The motion scoring scale has been used in prior studies and is described as follows: 1 = no motion artifact; 2 = minimal motion artifact, no effect on diagnostic quality; 3 = moderate motion artifact with some, but not severe, effect on diagnostic quality; 4 = severe motion artifact, images degraded but interpretable; and 5 = extensive motion artifact, images nondiagnostic.

13) Data and Safety Monitoring: An investigator will assign a serial code number and document pertinent clinical information. The code number assigned will not be derived from any personal identifier for the subject. The imaging exams and clinical data will have all patient identifiers removed, including the name, medical record number, and date of birth.

Subsequently, the imaging exams and clinical data will be labeled with a unique assigned code number. After all relevant information is recorded and the exams/data coded, the study coordinator will destroy the key linking any subject's personal history information to the assigned code number. Available coded clinical data will be reviewed following the completion of imaging exam evaluation. All data will be retained in a password-protected folder on a

research shared drive supported by DHTS. A formal data safety and monitoring board will not be used.

14) Privacy, Data Storage & Confidentiality: Every effort will be made to ensure subjects' confidentiality. All study files containing subject information will be kept on secure password protected computers with only study staff having access to the files. No identifying patient information will be included on any images or reported in any subsequent publications. Study data will be kept only for a period of six years after the study is completed, at which time all relevant study documents will be destroyed.

No identifiable PHI will be released outside of DUHS.

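### Does the undefined inclusion phrase in section 5 let consented patients with an unobtained image set drop out of the comparison?

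*Combined protocol and SAP*

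**What the plan says.** Section 5 (Selection of Subjects) sets the population as up to 100 consecutive adults having abdominal MRI and adds: "All subjects regardless of gender or race who had the appropriate imaging will be included". Section 6 places the consent discussion "just prior to the beginning of the examination", so nobody yet knows which sets will be obtained. Section 4 adds three triggered sets to the clinical examination: precontrast, portal venous and equilibrium.

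Section 12 says of the two readers: "They will assign motion scores and other measures of image quality between respiratory triggered and corresponding breath hold acquisitions". The worst motion grade is "5 = extensive motion artifact, images nondiagnostic". The test is the Wilcoxon rank sum. Section 12 also repeats the ceiling ("Up to 100 subjects will be included in the study population"), with no loss allowance and no separate analysis population.

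On data handling, section 4 says: "The clinical image data which are routinely sent to PACS will be deidentified and exported for offline analysis". The same sentence allows raw data to be kept in some cases for reprocessing. Once the relevant information is recorded, "the investigator will destroy the key linking any subject's personal history information to the assigned code numbers".

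**The concern.** The section 5 sentence is in the past tense and comes after consent in time. Read literally, it could require all three triggered sets, or at least one complete triggered/breath-hold pair, and so remove a consented patient whose set was aborted, failed to trigger or could not be reconstructed. Section 12 rates each triggered set against its breath-hold counterpart, so an absent set has no score.

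In these patients the loss could be informative. Section 3 says: "Particularly in ill patients, such as inpatients and those presenting to the Emergency Department, breath holding capacity may be diminished". If one technique fails more often and its failures go uncounted, that technique looks better than it is. Part of the stated purpose is to develop a single-breath-hold protocol, so whether the sets can be obtained at all is of interest. Once the link key is destroyed, the reason for a loss could not be traced unless someone had written it down.

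**Working it through.** **Text.** Three readings of the section 5 phrase are possible: the right kind of examination, all three triggered sets, or at least one complete pair. The first fits best. The sentence is built around gender and race, the sentence before it speaks of consecutive patients having abdominal MRI, and section 4 uses the same adjective for the scanner. Only the other two readings remove consented patients.

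Section 3 describes images that are hard to obtain at high quality. It does not describe images that are absent. Poor images that exist are scored, up to grade 5. What remains is the set never obtained, on which the plan is silent.

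**Arithmetic.** The plan has no figure to reproduce: it states no failure rate, effect size, power or loss allowance. Everything below is illustration on assumed inputs.

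*Assumed scores.* Grades 1 to 5 in 20, 35, 25, 15 and 5% of sets. Mean = 0.20×1 + 0.35×2 + 0.25×3 + 0.15×4 + 0.05×5 = 2.5.

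*Leaving lost sets out rather than scoring them 5.* The understatement of that technique's mean is f × (5 − 2.5), where f is the assumed share lost:

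| f | Understatement (grade) |
|---|---|
| 2% | 0.05 |
| 5% | 0.125 |
| 10% | 0.25 |
| 15% | 0.375 |

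*Requiring all three triggered sets.* Patients removed = 1 − (1 − f)³ if losses are independent, or f if they fall in the same patients. This gives 2 to 6% at f = 2%, 10 to 27% at f = 10% and 15 to 39% at f = 15%.

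*Effect on the comparison.* Simulation with 100 patients, one score per technique, latent correlation 0.3, 0.5 or 0.7, no true difference, 1,500 replicates. Ranges span the three correlations and repeated runs.

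| Assumed loss | Handling | Shift in mean difference (grade) | Rank sum rejection |
|---|---|---|---|
| None | – | about 0 | 0.1–3% |
| 10% of one technique, partly quality-related | incomplete pairs deleted | 0.03–0.09 | 0.1–4% |
| 10% of one technique, exactly the worst | incomplete pairs deleted | 0.07–0.16 | 0.4–10% |
| 10% of one technique, partly quality-related | all available scores | 0.10–0.11 | 2–5% |
| 10% of one technique, exactly the worst | all available scores | 0.22–0.23 | 12–19% |
| 5% of each technique | incomplete pairs deleted | about 0 | – |

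Handling matters because the rank sum test is unpaired and does not itself delete pairs. Its no-loss rejection rate is below 5% because it ignores the positive correlation within patients.

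The largest shift can be checked by hand. The worst 10% of sets are the 5% at grade 5 plus 5 of the 15 percentage points at grade 4. The remaining mean is (2.5 − 0.05×5 − 0.05×4) / 0.90 = 2.05 / 0.90 = 2.28, and 2.50 − 2.28 = 0.22. That case therefore needs every grade 5 set and a third of the grade 4 sets to vanish from one technique and none from the other. If those images were acquired, section 12 would score them 4 or 5 and the shift would disappear.

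**The case for a change.** The best case for a change is that the silence is real and cheap to end. Consecutive enrolment governs who is approached, not who stays in the analysis. Grade 5 covers only images that exist. The items that section 4 lists for recording (age, gender, indication, laboratory values) do not include a reason for a missing set, and section 10 wants the linking data destroyed as soon as possible. A reason code and a few sentences would settle the matter, and under one plausible handling the false-positive rate rises as far as 19%.

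Part of this stands. Reporting unobtained sets by technique, phase and reason is good practice, and a reason not noted at the scan may be lost. But a missing set can be counted from the coded examination without the key, and the key is destroyed only after relevant information is recorded. Kept raw data may also rescue some reconstruction failures. The 19% depends on an assumed extreme, one-sided loss that nothing in the documents supports. Feasibility appears in the purpose, but section 12 plans no feasibility rate that could be misreported.

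The obvious remedy also carries choices of its own. Grade 5 is defined by visible artifact, so giving it to an absent image departs from the scale. Technical failures would need a separate rule from breathing-related ones. If patients with lost sets count toward the ceiling, 2 to 15% loss on one side leaves 98 to 85 pairs per phase, with intervals wider by 1/√(1 − f), about 1 to 8%.

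**Conclusion.** No change is needed. The plan omits a missing-data detail, but nothing in it directs analysts to discard consented patients, and nothing shows that following it gives a wrong result. A sensible analyst would take section 5 to mean the relevant examination, score every acquired set including nondiagnostic ones, and state how many sets were not obtained.

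The possible bias is of unknown size and could favour either technique. At an assumed 10% one-sided loss it runs from 0.03 to 0.23 grade, depending on how closely loss follows quality and whether incomplete pairs are deleted. With equal loss of 5% per technique it is about zero. These figures rest on the assumed score distribution, correlations and loss rates, none of which the documents give. The conclusion would differ if losses proved frequent, one-sided and related to breathing; the documents offer no evidence of that.

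### Section 12 applies a test for independent samples to scores that come from the same patients, and sets no unit of analysis for two readers and three phases

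*Combined protocol and SAP*

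**What the plan says.** Section 4 (Design and Procedures) keeps the routine examination and adds to it: "we will acquire three extra image sets" (precontrast, portal venous and equilibrium), and "The only modification to the patients' clinical scan protocol will be to add these three image sets". Each patient is therefore imaged with both techniques in one session.

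Section 12 (Data Analysis and Statistical Considerations) describes the reading: "Two investigators will independently evaluate MRI examinations", and "They will assign motion scores and other measures of image quality between respiratory triggered and corresponding breath hold acquisitions". The motion scale is ordinal with five levels, beginning "1 = no motion artifact; 2 = minimal motion artifact, no effect on diagnostic quality". The only comparison method is this: "Comparisons between motion scores as well as other image quality scores will be made using the Wilcoxon rank sum test". The second reader is mentioned again only for agreement: "Inter-reader agreement will be assessed using the Interclass Correlation Coefficient". On size, "Up to 100 subjects will be included in the study population".

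Neither section says whether readers are averaged, read to consensus, analysed separately or pooled. Neither says whether the three phases are tested one by one or together.

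**The concern.** The rank sum test assumes that every score is independent of every other, within each technique and between techniques. Neither holds here. Two readers scoring one image share that image's artefact. Three phases from one patient share that patient's breathing. The triggered and breath-hold scores share the patient.

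Comparing image quality is one of the two stated purposes of the study (Section 2), so this test carries a main result. With no unit of analysis stated, the choice of reader, phase or pooling rule can be made after the scores are seen, and the error rate and power of the comparison depend on that choice.

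**Working it through.** **Count.** 3 phases x 2 readers = 6 scores per technique per patient, so 100 patients give up to 600 triggered and 600 breath-hold motion scores. This is a maximum: it assumes that every triggered set has a breath-hold counterpart and that both readers score everything.

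**Assumptions.** The plan gives no figure to reproduce: no significance level, power, effect size, variance or correlation. I take a two-sided 5% level. I split the variance of a latent score (total 1) into patient, shared by both techniques (va); patient-by-technique (vb); image (vc); and reader error (ve).

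**Variance ratios.** For each way of using the rank sum test, divide the true variance of the difference between techniques by the variance the test assumes. Above 1 there are too many false positives; below 1, too few.

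- All six scores pooled: true (2/n)(vb + vc/3 + ve/6), assumed 2/(6n). Ratio = 6vb + 2vc + ve. Because the shares sum to 1, it exceeds 1 only when 5vb + vc > va.
- Two readers pooled in one phase: ratio = 2vb + 2vc + ve, above 1 only when vb + vc > va.
- One reader, one phase: ratio = vb + vc + ve = 1 - va, never above 1.

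Example for six pooled scores with shares 0.4/0.1/0.2/0.3: ratio = 0.6 + 0.4 + 0.3 = 1.3, and 2[1 - Φ(1.96/√1.3)] = 8.6%. The simulation gave 9.25%.

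**Null simulation.** Scores of 1-5, 100 patients, 2,000 runs per setting (Monte Carlo standard error about 0.5 points at 5%). Entries are the percentage of runs with p < 0.05. The last column is the signed-rank test on each patient's mean difference over readers and phases.

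| va/vb/vc/ve | Ratio, six pooled | Rank sum, six pooled | Rank sum, two readers, one phase | Rank sum, one reader, one phase | Signed-rank, patient mean |
|---|---|---|---|---|---|
| 0.7/0/0/0.3 | 0.30 | 0.15 | 0.15 | 0.05 | 4.8 |
| 0.6/0/0.2/0.2 | 0.60 | 1.5 | 1.55 | 0.7 | 4.95 |
| 0.5/0.05/0.2/0.25 | 0.95 | 5.5 | 3.55 | 1.15 | 5.45 |
| 0.6/0.1/0.1/0.2 | 1.00 | 5.75 | 1.4 | 0.35 | 4.5 |
| 0/0/0/1 | 1.00 | 4.25 | 4.0 | 4.65 | 3.9 |
| 0.4/0.1/0.2/0.3 | 1.30 | 9.25 | 3.9 | 1.7 | 4.95 |
| 0.1/0/0.6/0.3 | 1.50 | 10.8 | 11.0 | 4.5 | 5.4 |
| 0.3/0.3/0.2/0.2 | 2.40 | 20.55 | 7.45 | 2.45 | 5.45 |
| 0.2/0.4/0.2/0.2 | 3.00 | 22.95 | 8.15 | 2.5 | 4.5 |
| 0/0.5/0.25/0.25 | 3.75 | 27.35 | 11.45 | 4.25 | 4.75 |

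With 50 patients the pattern is the same: 0.4% to 27.3% for six pooled scores, and 3.85% to 6.35% for the patient-level test.

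**Power in one phase.** Assume a latent shift of 0.25 SD and 100 patients, so 0.25/√(2/100) = 1.768.

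- Rank sum, one reader: Φ[(1.768 - 1.96)/√(1 - va)]. Equal shares (0.25 each): Φ(-0.22) = 41%. Shares 0.6/0.1/0.1/0.2: Φ(-0.30) = 38%.
- Paired, readers averaged: Φ[0.25/√(2(vb + vc + ve/2)/100) - 1.96]. Equal shares: Φ(2.236 - 1.96) = 61%. Shares 0.6/0.1/0.1/0.2: Φ(3.227 - 1.96) = 90%.

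Simulation on the five-category scale runs slightly lower: about 33-38% and 48-85% across the splits tried. Part of the gain comes from the second reader. With equal shares the variance of the paired difference falls from 2 x 0.75 = 1.50 to 2 x 0.625 = 1.25, or 17%.

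**Changing only the test.** A signed-rank test on all pooled scores has ratio (6vb + 2vc + ve)/(vb + vc + ve), which is never below 1. With equal shares it is 2.25/0.75 = 3.0, and simulation gave 22-24% false positives. Pairing alone does not settle the unit of analysis.

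**The case against.** The strongest reply is that nobody has said the scores will be pooled. Section 12 speaks of comparisons in the plural and of matching each triggered acquisition to its breath-hold counterpart. That fits separate tests by phase and reader at least as well as one large pooled test, and separate tests do not inflate the error rate of any one test. A reader might infer that the plan enters 600 against 600 scores as if they were independent patients, so that its p-values are too small. The documents do not support this: pooling is not stated.

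Inflation would not be certain even with pooling. A patient effect common to both techniques cancels in the difference, and an unpaired test that ignores this is conservative. Which force is larger depends on variance shares that the documents do not give. Both parts of this objection stand.

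What it does not rescue is the choice of test. On the reading that avoids inflation, the rank sum test discards the pairing and, with one reader, the second reader's information as well. It also leaves two answers per phase and no rule for choosing between them.

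A further objection, that averaging ordinal scores treats categories as equally spaced, is fair and is a real limit of the proposed remedy.

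**Conclusion.** The point holds as a mismatch between test and data together with an undefined unit of analysis. It does not hold as a finding that the plan inflates false positives. If all scores were pooled, the rank sum error rate could lie anywhere from about 0.2% to 27% at a nominal 5%, and the documents do not show where. With one reader and one phase it is at or below nominal (0.05% to 4.65% in the settings above), and power is well below that of the paired, reader-averaged comparison.

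The count of up to six scores per technique and the pairing within patient follow from Sections 4 and 12. The percentages rest on assumed variance splits, a 5% two-sided level, 100 patients and, for power, a 0.25 SD shift. The direction of the single-reader result does not depend on the split: its variance ratio is 1 - va, which equals 1 only if the techniques share no patient variation. The plan should be changed because a better method needs no further data.

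**What to change.** In Section 12, replace the rank sum sentence with text that:

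- names the patient as the unit of analysis;
- averages the two readers' scores for each image set;
- compares triggered with breath-hold within patient by a signed-rank test on the patient's difference, one comparison per phase;
- for any overall result, averages the three phases within patient first, or fits an ordinal mixed model with patient, image and reader effects;
- says in advance whether the overall result or a given phase is the main comparison;
- reports each reader's results alongside.

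The same rule should cover the other image quality scores. The agreement coefficient stays as a separate report.

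The cost is a few sentences and no extra imaging or reading beyond two readers scoring each image. There are two downsides. Averaging treats the 1-5 scale as roughly interval; the ordinal model avoids this at the price of a more complex fit. P-values may also be less favourable than those from pooled scores.

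### The plan has two investigators score subjective image quality for the main comparison and describes neither masking to acquisition technique nor a randomised reading order.

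*Combined protocol and SAP*

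**What the plan says.** Section 2 names the image quality comparison in the study purpose: "To develop a single breath hold abdominal MRI protocol, and compare the image quality of respiratory triggered 3D" T₁-weighted images against conventional breath hold images. No endpoint is formally labelled primary, but this is the only comparison the analysis section describes.

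Section 12 sets out the reading: "Two investigators will independently evaluate MRI examinations", and then "They will assign motion scores and other measures of image quality between respiratory triggered and corresponding breath hold acquisitions". The motion score is a five-category judgement running from no artifact to nondiagnostic images. The other quality measures are not defined. For the analysis, "Comparisons between motion scores as well as other image quality scores will be made using the Wilcoxon rank sum test", and "Inter-reader agreement will be assessed using the Interclass Correlation Coefficient".

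Three other provisions come near the subject of masking:

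- Section 4, on export: "The clinical image data which are routinely sent to PACS will be deidentified and exported for offline analysis". The identifiers listed for removal are name, medical record number and date of birth.
- Section 4, on coding: "the individual MRI examinations and clinical information will be labeled with a unique assigned code number".
- Section 13, on timing: "Available coded clinical data will be reviewed following the completion of imaging exam evaluation".

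The document does not mention masking to technique, removal of sequence labels, reading order, or whether the two sets of a pair are read together or apart.

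**The concern.** The readers are members of the study team, and Section 3 presents the new sequence as a possible route to a liver protocol with a single breath hold. The boundaries between score categories (minimal, moderate, severe) are matters of opinion. A reader who knows which technique produced an image can score it according to expectation without intending to, and two readers with the same expectation will lean the same way.

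If that happened, the estimated difference would combine the true difference with the shared leaning, and reanalysis of those scores could not separate them. The agreement coefficient gives no protection because it measures how closely the readers agree with each other. Two readers who share a bias can agree well.

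**Working it through.** **Do the stated safeguards hide the technique?** Taking each in turn:

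| Provision | What it protects | Hides technique? |
|---|---|---|
| Independent reading (Section 12) | Each reader from the other's influence | No |
| Removal of patient identifiers (Sections 4, 13) | Patient identity; sequence labels are not mentioned | No |
| Code number per examination (Section 4) | Patient identity; one examination holds both techniques, so they share a code | No |
| Clinical data reviewed after image evaluation (Section 13) | The reading from clinical context | No |
| Inter-reader coefficient (Section 12) | Measures agreement only | No |

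**How much could a shared shift matter?** The plan has no figure to reproduce. It gives a cap of 100 subjects and no alpha, power, effect size or SD. What follows is an illustration, and every input except the cap is assumed.

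Inputs: n = 100 pairs; no true difference; SD of the paired difference SDd = 0.8, 1.0 or 1.2; within-patient correlation ρ = 0.3 or 0.5; two-sided 5%; shared shift b = 0, 0.15 or 0.25 points; one score per patient per technique.

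The planned rank sum test ignores the pairing. Under a normal approximation:

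- SD of a single score: s = SDd / √(2(1 − ρ))
- Critical difference: c = 1.96 × s × √(2/n)
- True standard error of the mean difference: SE = SDd / √n
- Probability of a false positive: P = Φ((b − c)/SE) + Φ((−b − c)/SE)

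Worked case, SDd = 1.0, ρ = 0.3, b = 0.25: s = 1/√1.4 = 0.845; c = 1.96 × 0.845 × √0.02 = 0.234; SE = 0.100. The first term is Φ(0.16) = 0.56 and the second is negligible, so P ≈ 0.56.

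| ρ | b | SDd 0.8 | SDd 1.0 | SDd 1.2 |
|---|---|---|---|---|
| 0.3 | 0 | 0.019 | 0.019 | 0.019 |
| 0.3 | 0.15 | 0.320 | 0.200 | 0.137 |
| 0.3 | 0.25 | 0.783 | 0.563 | 0.398 |
| 0.5 | 0 | 0.006 | 0.006 | 0.006 |
| 0.5 | 0.15 | 0.185 | 0.102 | 0.064 |
| 0.5 | 0.25 | 0.638 | 0.393 | 0.246 |

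The rate without a shift is below 5% because an unpaired test is applied to paired data. To see the effect of the shift alone, use a paired normal test (replace c by 1.96 × SE). It gives 0.05 with no shift; 0.466, 0.323 and 0.240 for b = 0.15; and 0.878, 0.705 and 0.549 for b = 0.25.

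**Five-category checks by simulation.** With assumed score distributions of 20/35/25/15/5% and 30/40/20/8/2%, score correlation of about 0.3 and 0.5, and random one-category improvements, the rank sum test was falsely significant in 0.5–1.9% of runs with no shift, 9–18% at a mean shift of 0.15 and 32–50% at 0.25.

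A separate simulation used the 20/35/25/15/5% distribution and latent correlation 0.3 to 0.7. It lowered the respiratory triggered score by one category in 20% or 30% of images. Because 20% of scores already sit at 1, the mean shifts are 0.8 × 0.20 = 0.16 and 0.8 × 0.30 = 0.24. The rank sum rates were 7–14% and 29–35%; the signed-rank rates were 20–36% and 43–67%.

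**The case against.** The best reply is that the plan is silent rather than committed to unmasked reading. It does not say that readers see sequence labels or view pairs side by side, and masking may be done in practice. That is correct, and nothing here shows that any reading was or will be biased. But a plan whose conclusion rests on reader judgement has to state how the readers are protected, and none of its steps would conceal the technique.

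The illustration can also be criticised. Its inputs are assumed, and a span of 6% to 78% is too wide to serve as an estimate. It also simplifies the design: Section 4 adds three respiratory triggered sets per patient, there are two readers, and how phases and readers are combined is not stated. These points stand. The figures show only that a shift of a fraction of one category could matter.

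The statement that a shared shift leaves agreement unchanged is exact only for a constant shift within one technique. Scores here are bounded whole numbers. In one check on assumed inputs (latent inter-reader correlation 0.75, mean shift 0.25, improvements independent between readers) the within-technique coefficient fell from about 0.69 to 0.59. A fall of that kind still would not reveal a shared bias.

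Finally, the sequences may look different enough to be recognised without labels, and a masked re-read of retained images could be done later. The first limits the remedy but does not remove its value. The second is possible but not planned.

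**Conclusion.** The concern holds. No section masks the two investigators to technique, sets a reading order or describes how pairs are presented, although the comparison named in the study purpose depends on their subjective scores. That conclusion comes from the text alone and needs no numerical assumption.

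The size and direction of any bias cannot be determined from the document. On the assumed inputs, a shared shift of a quarter of a category raises the false-positive rate of the planned test from about 1–2% to 25–78%, or to 32–50% in the matching five-category simulation. This should be corrected before reading begins. Confidence is medium, because actual bias is unproven and masking may be only partly achievable.

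**What to change.** Amend Section 12 to state that:

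1. Each image set is exported with sequence name and acquisition annotation removed, and carries its own code at image-set level.
2. Sets are presented one at a time in computer-randomised order. The two sets of a pair are not read side by side and preferably fall in separate sessions.
3. Both readers score without being told the technique.
4. If the sequences can be recognised by appearance, incomplete masking is reported as a limitation. Recording each reader's guess of the technique is optional.

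The cost is small. A de-identified export is already planned, so label removal and set-level codes can be added there, together with a randomised reading list. Reading will take somewhat longer. No extra readers or scans are needed.
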